ACTIVITY	PRENATAL VISITS (approximate week gestation)			
	1st *	2nd (26wk)	3rd (32 wk)	4th (38 wk)
Recommendations for: urgent consultation next visit/schedule treatment/medical conditions	■	■	■	■ date of wk 41 and instructions
Referral to hospital if needed	⊗	⊗	⊗	⊗
Detection of breech presentation & referral for external version	—	—	—	■
Instruction for referral for adequate level of delivery	—	—	⊗	⊗
Recommendations for lactation			■	■
Contraception	—	—	■	■
Pre-conceptual care	—	—	—	⊗
Activities to reduce smoking	■	■	■	■

■ for all women * for all women at first contact with clinic, regardless of gestational age ⊗ only in some cases: delivery: if previous obstructed labor, hemorrhage or C.S.; pre-conceptual care: infant with NTD or other congenital malformation
				

Table 4 : BASIC ANTENATAL CARE PLAN BY VISIT

The First Visit

- Medical/Ob history (risk evaluation)
- Clinical examination / severe anemia
- Ob exam / Gyn exam (can be postponed until second visit)
- Maternal weight / height
- Blood pressure
- Gestational age estimation
- Uterine height
- Syphilis, detection of symptomatic STDs
- Urine test (multiple dipstick)
- Tetanus toxoid
- Fe / Folic acid supplementation
- Recommendation for urgencies / hot line for emergencies
- Complete antenatal card
- Blood type and Rh

The Second Visit and subsequent visits

- Blood pressure to nulliparous & women with previous preeclampsia/age groups
- Obstetric exam
- Gestational age estimation
- Fetal heart rate
- Uterine height
- Urine test (only nulliparous/women with previous preeclampsia)
- Fe / Folic acid supplementation
- Clinical examination for anemia
- Maternal weight (only women with low weight/height 1st visit)
- Recommendation for urgencies
- Complete antenatal card

For the Third Visit - add:

- Repeat syphilis & g.c. test for high-risk women
- Hb
- Tetanus toxoid (second dose)
- Instructions for adequate place of delivery
- Recommendations for lactation / contraception

For the Fourth Visit - add:

- Detection of breech presentation & referral for external version

Furthermore, a recent attempt was made to evaluate the items which could mediate the relationship between routine prenatal care and birth weight. There were eight activities considered necessary to be included in prenatal care to achieve an impact on LBW: risk assessment, urine culture, smoking cessation, alcohol and drugs avoidance, low weight and referral, follow-up of no shows and weight gain monitoring (Petitti et al., 1991). The new model includes most of them except weight gain, which is recommended to a subgroup of women; although it does not recommend routine urine culture, it has one rapid screening mechanism for bacteriuria.

[figure not shown]
Flow Chart: Figure 2 presents the Flow Chart of patients enrolled in the new programme and the two levels of care available. At the first antenatal visit in the clinics randomized to the system, patients will be asked to provide informed consent to participate in the study. Those who agree to do so will be classified as to whether or not they require special care (classifying form). It is very likely that clinics already have a risk score system, which will have to be replaced by Classifying form only in those clinic randomized to the new programme.

Women eligible for the basic component of the new programme can be referred, if needed, to a nutrition clinic, psychiatric unit or to a tertiary hospital for delivery. Women with only risk factors for delivery complications but with normal pregnancies will follow the basic component of the new programme. It is considered that no additional prenatal visits are needed for women requiring social or nutritional support; this also is the same for women with only a history of intrapartum complications.

Women who are not eligible for the basic component of the new programme (from "classifying") will receive care either at a referral hospital or evaluated at the same clinic by a consultant. The decision of the place and content of care for these patients will be based on current medical practices in the study sites. Table 5 presents an example of patient flow analysis for a clinic recruiting 550 patients in a 12-month period. In such a case, it is expected that each clinic will have an approximate total of 200 pregnant patients (new and continuing) in the month of highest recruitment, plus extra visits for high risk patients as

Figure 2 :

WHO Antenatal care randomized trial; flow chart of patients enrolled in clinics *randomized to the intervention group*

WHO 96051

Table 5 : PATIENT FLOW ANALYSIS : ANTENATAL CARE TRIAL

Month	VISIT				Total Clinic visits
	First	Second S + US	Third S + US	Fourth S + US	
1	46				46
2	46				46
3	46				46
4	46	44 + 5			95
5	46	44 + 5	42 + 6		143
6	46	44 + 5	42 + 6	40 + 8	191
7	46	44 + 5	42 + 6	40 + 8	191
8	46	44 + 5	42 + 6	40 + 8	191
9	46	44 + 5	42 + 6	40 + 8	191
10	46	44 + 5	42 + 6	40 + 8	191
11	46	44 + 5	42 + 6	40 + 8	191
12	46	44 + 5	42 + 6	40 + 8	191
13		44 + 5	42 + 6	40 + 8	145
14		44 + 5	42 + 6	40 + 8	145
15		44 + 5	42 + 6	40 + 8	145
16			42 + 6	40 + 8	96
17				40 + 8	48
18					
Total	552	588	576	576	2292

Assumes: 12 months to recruit 550 women (46 per month)
 First visit at 12 weeks
 Second visit at 26 weeks, plus 10% unscheduled visits.
 Third visit at 32 weeks, plus 15% unscheduled visits.
 Fourth visit at 38 weeks, plus 20% unscheduled visits.

medically required and who are not referred to the hospital. It is recommended that each study site construct similar flow analysis adapted to their average clinic size.

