The first visit should occur ideally in the first trimester, around the 12th week of pregnancy. However, all pregnant women initiating prenatal care in the intervention clinics regardless of their gestational age will be examined following the norms for the first visit and enrolled in prenatal care at that time. The first visit examination is expected to take 30-40 minutes. Emphasis is placed on the medical and obstetric history. Objective findings at examination give additional or confirmatory evidence. While the case history, proposed conforms to and even exceeds traditional standards, the elements of the physical and biochemical examinations are fewer and less resource-demanding than those commonly used.

Pregnancy tests are widely used and abused by the health system and women. In the U.K. it is reported that up to seven pregnancy tests are performed for each live birth (Voss, 1992). Pregnancy tests will be provided at the clinic to women during the first trimester and results given to women who request reassurance that they are pregnant if there are no signs or symptoms of pregnancy. In countries where abortion is legal, women may request a pregnancy test if they are planning an abortion and do not trust a negative clinical judgement.

Social, educational and work components help to identify risk. Work may be physically hard, and it may give exposure to teratogenic agents (heavy metals, toxic chemicals, ionizing radiation). Women could be advised and provided with the required documentation to reduce work if it is very hard or it requires long standing positions (Launer et al., 1990). The feasibility of classifying women by social class indicators and providing additional family support to very poor women could be considered at some study sites, as the hard work/negative pregnancy outcome relationship appears to be related to social class (Klebanoff et al., 1991; Barnes et al., 1991).

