Only one routine vaginal examination during pregnancy is recommended, including taking a sample for Pap smear if this is routinely performed in the clinics and screening for symptomatic STDs (Wangford & Smaill, 1989). It could be postponed until the second visit if the doctor or midwife feels that the women or her companion would not accept this. In women with (a history of) bleeding in the present pregnancy, vaginal examination should not be performed at the clinic after the first trimester, and the patient should be referred for ultrasonography examination, if available at the hospital, to exclude placenta previa (Chamberlain, 1992).

As routine iron supplementation will be given to all women, hemoglobin would be determined only at 32 weeks (the third visit) unless there are clinical signs of anemia.

Easy access to care in case of need is essential in the new package. This must be guaranteed through written information about which place and which person to contact, with telephone numbers if available, on a 24-hour basis.

Individual instruction is an essential element of antenatal care. Sufficient time must be set aside for communication and planning, especially at the first visit. We anticipate more available time for each individual visit as a result of the lower number of visits for low risk (the majority of) women, in addition to shorter waiting times and immediate medical availability for unscheduled visits. It will include general information about pregnancy and delivery and individual counselling if demanded or deemed necessary. Otherwise, patients can

go home sooner. The individual counselling will be specific to each woman's condition and emphasis will be on listening to her problems. It should include simple written instructions in the local language, even to illiterate mothers (often family members or neighbors can read). This activity will be focused on instruction for actions to be taken in case of pregnancy-related emergencies. Less emphasis will be placed on formal social support or general health education, as several randomized controlled trials have failed to demonstrate major benefits (Oakley, 1990; Villar et al., 1992).

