- third stage excessive bleeding
- puerperal sepsis
- gestational diabetes

III.C. Special perinatal (fetal, newborn) complications and events in previous pregnancies (specify and validate as for III.B.):

- twins, higher order multiples
- low birth weight (LBW): < 2500 g, or to be defined
- intrauterine growth retardation (if feasible)
- rhesus-antibody affection (erythroblastosis, hydrops)
- malformed, chromosomally abnormal child
- macrosomia (> 4500 g) newborn
- resuscitation, other treatment of newborn
- perinatal, neonatal, infant death (also: later death).

IV. History of present pregnancy

- IV.A. Date of last menstrual period (LMP). Certainty of dates (by regularity and accuracy of recall, other relevant information).
- IV.B. Habits: smoking/chewing tobacco, alcohol, drugs (frequency, quantity).
- IV.C. Any untoward events (pain, vaginal bleeding of threatened miscarriage, hemorrhage).
- IV.D. History of malaria attacks.

V. Physical examination

- V.A. Weight and height; blood pressure (BP). Chest, heart auscultation, Symphysis to fundus distance (in centimeters). All women.
- V.B. Signs of severe anemia: complexion, fingernails, conjunctiva, oral mucosa, tip of tongue. Shortness of breath. All women.
- V.C. Consider vaginal examination, especially if untoward events are positive (IV.C)

VI. Special tests

- VI.A. Urine: protein, multiple dipstick for bacteriuria.
- VI.B. Blood: syphilis (rapid test) result while waiting in the clinic. If positive: treat.
Hb: only if signs of severe anemia.
Blood type and rhesus.

VII. Assessment and referral

- VII.A. Determine the expected date of delivery based on LMP and all other relevant information. Use 280-day rule (LMP + 280 days). Observe: same women will refer to the date of the first missed period when asked about LMP, which may lead to miscalculation of term by four weeks.
- VII.B. Risk assessment (advice: see IX): Women are classified as eligible for the basic components of the new antenatal package or in need of special care and to be followed at the clinic or hospital (Classifying form, Appendix I).

For the following conditions, if diagnosed, is recommended:

- diabetes: refer, must have continued higher level care
- heart disease: refer
- renal disease: refer
- epilepsy: advice on continued medication
- drug abuse: special care
- signs of severe anaemia and Hb < 70 g/dl: higher iron dose, or refer if shortness of breath
- HIV positive: counsel on risk to offspring; refer

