It is very likely that a good number of women will not initiate antenatal care early enough in pregnancy to follow the schedule presented above. These women, particularly those starting > 32 weeks of gestation, should have the first visit with cumulative activities of previous visit and after it the ones which correspond to the gestational age. It is expected therefore that the first visit will take more time than a regular first visit. Special care should be taken that all previous activities are conducted at this time.

The Post-Partum Visit

Although the post-partum visit is universally recommended for perinatal care, it is seldom done in most developing countries. The importance of this "post" and "pre-conception care" visit has been recently emphasized by the expert panel on prenatal care (Rosen et al., 1991). The determinants of some pregnancy outcomes, such as low birth weight and the

Table 3 : CONTENT OF THE BASIC COMPONENT OF THE
NEW ANTENATAL CARE PROGRAMME

ACTIVITY	PRENATAL VISITS (approximate week gestation)			
	1st *	2nd (26 wk)	3rd (32 wk)	4th (38 wk)
Pregnancy test (only if req. at 1st trimester & no clinical evidence of preg.)	☒	--	--	--
Medical/Ob history (risk evaluation)	■	--	--	--
Question of Rh immunization with fetal/newborn disease in previous pregnancy	☒ multiparous	--	--	--
Complete clinical examination	■	--	--	--
Clinical examination for severe anemia	■	■	■	■
Ob exam (+) Gyn exam/detection of symptomatic STDs	■ routine vaginal exam **	■ ob exam	■ ob exam	■ ob exam
Maternal weight/height	■	--	--	--
Maternal weight (follow-up)	--	☒	☒	☒
Uterine height	■	■	■	■
Gestational age assessment	■	■	■	■
Blood pressure	■	■	■	■
- Blood type / Rh	■	--	--	--
- Hb	☒	☒	■	--
- Syphilis	■	--	--	--
- Urine test	■ ***	☒	☒	☒
Tetanus toxoid	■	--	■	--
Folic acid/Iron supp.	■	■	■	■
Fetal heart rate	☒	☒	☒	☒

■ for all women
 * for all women at first contact with clinic, regardless of gestational age
 ** could be postponed to second or third visit
 ☒ only in some cases:
 a) proteinuria: nulliparous or with previous preeclampsia or hypertension;
 b) fetal heart rate: only if requested or no fetal movements seen or reported;
 c) maternal weight: only those with low weight/height at 1 visit or obese women
 d) anemia: ☒ only if signs of severe anemia
 *** multiple dipstick
 (+) ob exam: # fetuses, fetal situation & presentation

Table 3 : CONTENT OF THE BASIC COMPONENT OF THE
NEW ANTENATAL CARE PROGRAMME
(cont'd)

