4.15 Ethical issues

There are two main ethical issues related to the proposed trial: the first is the issue of reducing the number and content of antenatal visits from the standard, well-accepted antenatal care system as is recommended at the present time; the second is related to the mechanisms to obtain the informed consent of the participating women.

In relation to the first, we do not think there are violations of the rights of women for the following reasons:

- (a) The content and timing of visits presently recommended for normal, health pregnant women have not been scientifically evaluated, and relate mainly to traditional practice and some economical considerations. Two major international groups have extensively reviewed the situation in the USA and Europe, and have recommended the need for a systematic evaluation of prenatal care (Rosen, 1991; Lindmark, 1991). Furthermore, as discussed in sections 5 and 6.4 of the protocol, some of the present practices, such as routine ultrasound measures, measure of biparietal diameter with ultrasound after 20 weeks for gestational age dating, glucose tolerance test for screening for gestational diabetes, and measuring hemoglobin at every antenatal visit, have been demonstrated to be of limited value (Chalmers, 1989). Some practices may even be harmful (maternal weight restriction or routine vaginal examination). A recent comprehensive review of antenatal care stated that "visits that are not meaningful are counter-productive" (Rosen, 1991). We are proposing to include in the programme only those activities proven or strongly suggested to be beneficial to women and their babies (U.S. Public Health Service Expert Panel, 1989; Petitti et al., 1991).
- (b) Most women attending prenatal care in public clinics in developing countries do not receive, nor will they in the near future, the traditional "recommended" antenatal care programme. Present care is unevenly distributed, haphazardly allocated, and the visit length is clearly insufficient. The new system should allow health care providers to devote more time to the activities which are proven effective.

- (c) Medical conditions present before pregnancy or related to pregnancy will be referred and treated as presently recommended by local obstetrical practice for high risk patients.

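### For women with bleeding whose first visit falls after the first trimester, the first-visit narrative rules out a vaginal examination at the clinic, while item V.C steers staff towards one

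*Protocol*

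**What the plan says.** All of this concerns the new programme (Protocol, section 4.4.2) and the forms built from it.

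- **Narrative, The First Visit.** One routine vaginal examination is recommended in pregnancy. It may be put off to the second visit if the woman or her companion would not accept it. Then comes a restriction: "In women with (a history of) bleeding in the present pregnancy, vaginal examination should not be performed at the clinic after the first trimester". Such women are to be sent for an ultrasound scan, where the hospital has one, to rule out placenta praevia.
- **Content of the first visit, V.C.** "Consider vaginal examination, especially if untoward events are positive (IV.C".
- **Content of the first visit, IV.C**, to which V.C refers. "Any untoward events (pain, vaginal bleeding of threatened miscarriage, hemorrhage".
- **Who the first-visit content covers.** Every woman entering care at an intervention clinic, "regardless of their gestational age will be examined following the norms for the first visit". The paragraph on late attenders expects many of them: "It is very likely that a good number of women will not initiate antenatal care early enough in pregnancy".
- **Table 3** marks the routine vaginal examination with its symbol for all women at the first visit. Its footnote says it "could be postponed to second or third visit".
- **Table 4 and the basic antenatal care checklist (Appendix I)** list the gynaecological examination at the first visit and allow it to be postponed to the second visit only. The checklist also tells staff seeing a late booker to catch up on everything due by then.

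**The concern.** The narrative treats bleeding after the first trimester as a reason not to examine at the clinic. V.C treats bleeding as a particular reason to think about examining, and sets no gestational-age limit. Neither item refers to the other, and nothing says which governs.

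The restriction is worded as a safety precaution, yet it appears only in running prose. The itemised list, both summary tables and the checklist omit it. The section on implementation in Khon Kaen says the checklist was built into the medical record, so the page closest to daily care is one that lacks the restriction. What is at stake is uniform delivery of the intervention, which section 4.1 calls crucial, and the care of a small group for whom the protocol itself set a precaution.

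**Working it through.** The plan gives no figure on this point to reproduce. The check is a comparison of texts, followed by one proportion for scale.

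**Step 1: which women fall under conflicting instructions.**

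| Woman at her first visit | Narrative | Item V.C | Compatible? |
|---|---|---|---|
| First trimester, bleeding | Restriction does not apply | Consider, especially | Yes |
| Any gestation, pain only | Restriction does not apply | Consider, especially | Yes |
| After first trimester, no IV.C event | One routine examination recommended | Consider | Yes |
| After first trimester, bleeding now or earlier in this pregnancy | Not at the clinic; refer for scan | Consider, especially | **No** |

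Only the last row conflicts. It is a real group, because first-visit norms apply at any gestational age.

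**Step 2: does another staff-facing page resolve it?**

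- Table 3: marked for all women; no bleeding exception.
- Table 4: listed; no bleeding exception.
- Checklist: listed, with catch-up for late bookers; no bleeding exception.

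None does. They also differ on postponement. The narrative, Table 4 and the checklist allow the second visit; Table 3 allows the second or third. Table 3 places those visits at 26 and 32 weeks, both beyond the first trimester.

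**Step 3: how common is a late first visit?** Inputs are from Table 22 (Khon Kaen, both arms pooled): 2,354 women at less than 12 weeks, 3,306 at 12 to 28 weeks, 894 at more than 28 weeks, 6 missing; total 6,560. Section 5.2.3 treats the first of these bands as the first trimester.

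- First visit at 12 weeks or later: 3,306 + 894 = 4,200.
- Share: 4,200 / 6,560 = 64.0%.

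**Step 4: can the overlap with bleeding be counted?** Section 5.2.4 reports 136 women with vaginal bleeding: 65 in the first trimester, 33 in the second and 38 in the third. These are counts over the whole pregnancy and are not cross-classified by gestational age at the first visit. The number in the conflicting row therefore cannot be derived.

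**The case against.** The strongest reply is that the two texts can be read together. V.C only asks staff to consider an examination and mandates nothing, and a specific restriction in the same section can be taken to limit a permissive general line. The IV.C wording on threatened miscarriage, and an ideal first visit around week 12, point to early pregnancy, where the texts agree. This narrows the conflict to one row of the table but does not remove it. IV.C also names haemorrhage without a trimester, and V.C singles out the very women whom the narrative restricts.

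A second reply is that not everything staff used is visible. The Manual of Clinical Activities is not part of the document, nor is the content of the classifying form. The checklist's first line concerns eligibility on that form, and women found ineligible are managed by local practice. The first-visit list is incomplete in the copy reviewed, and the lists for later visits do tell staff to refer women who bleed. All this stands as a limit: the protocol's pages conflict as printed, but it is not shown that any woman was examined against the narrative.

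Three stronger readings are tempting, and the document does not support them.

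- A reader might take the women who bled in the second or third trimester (33 + 38 = 71 of 136) as the number affected, or scale that up to the whole trial. V.C applies at the first visit only. The 71 include women who booked early and bled later, and they leave out women who bled early and booked late, whom the narrative also covers. The figure is neither an upper nor a lower bound.
- A reader might set section 4.15, "Some practices may even be harmful (maternal weight restriction or routine vaginal examination", against the programme's own examination. That remark criticises present practice, and a programme limited to one routine examination is consistent with it.
- A reader might see postponement beyond the first trimester as a breach of the restriction. For women without bleeding it is not, since the restriction does not cover them.

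**Conclusion.** The contradiction holds for one defined group: women with bleeding, or a history of bleeding, in the present pregnancy whose first visit comes after the first trimester. For them the narrative and V.C point in opposite directions, and Table 3, Table 4 and the checklist do not settle the matter. The disagreement over postponement is a lesser, editorial inconsistency about the same examination.

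Late booking is frequent enough (64% in Khon Kaen) for the overlap to be realistic, but its size is unknown. The 64% rests on taking 12 weeks as the trimester boundary, as the report does, and says nothing about the other three sites.

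This is a correction to how the intervention is specified. It does not threaten the trial's inference: neither primary outcome definition, nor the sample size, nor the analysis depends on it. It should be corrected, but it ranks below faults that bear on those elements. No view is taken here on which clinical rule is right.

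**What to change.** Reconcile five places in the protocol into a single rule chosen by the investigators: the First Visit narrative, item V.C of the first-visit content, Table 3 with its footnote, Table 4, and the Appendix I checklist. Whatever restriction by bleeding and gestational age they settle on should be stated in the content list and on the checklist as well as in the narrative. The same edit should settle whether the examination is for all women or for consideration, and to which visit it may be postponed. The Manual of Clinical Activities should be checked against the result.

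The cost is a few lines of wording, plus a short notice to any intervention clinic still applying the programme. In Khon Kaen recruitment closed on 30 April 1997 and follow-up ended on 31 October 1997, so a notice there would come too late. For that site the use of the correction is an accurate description of the model in reports and in any later adoption.
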